6.3 Known Undesirable Effects of Study Drug/Treatment

Overall, safety data available from completed, controlled and uncontrolled studies indicate that everolimus is generally well tolerated at weekly or daily doses. The safety profile is characterized by manageable adverse events (AEs). These AEs are generally reversible and non-cumulative.

Adverse events most frequently observed with everolimus are stomatitis, mouth ulcers, acne, infection, and menstrual irregularities. Adverse events that are also common include: rash, diarrhea, fatigue, asthenia, nausea, peripheral edema, decreased appetite, headache, dysgeusia, epistaxis, mucosal inflammation, pneumonitis, weight decreased, vomiting, pruritus, cough, dyspnea, dry skin, nail disorder, aggression, and pyrexia.

Overall, the most frequently observed laboratory abnormalities include: decreased hematology parameters including hemoglobin, lymphocytes, platelets, and neutrophils; increased clinical chemistry parameters including cholesterol, triglycerides, glucose, aspartate transaminases, creatinine, alanine transaminases, and bilirubin; and decreased clinical chemistry parameters including phosphate and potassium.

The majority of these AEs have been of mild to moderate severity (NCI CTC grade 1-2). Recommendations for dose adjustments, should any of these treatment related adverse events occur, are given in Table 3.

6.3.1 Adverse Drug Reactions (ADRs) Reported for Previous Tuberous Sclerosis Complex Studies

The most frequent ADRs (incidence \geq 1/10 and suspected to be related to treatment by the investigator) from the pooled safety database are (in decreasing order): stomatitis, amenorrhea, upper respiratory tract infections, hypercholesterolemia, nasopharyngitis, acne, menstruation irregular, sinusitis, and pneumonia

The most frequent grade 3/4 adverse reactions (incidence \geq 1/100 to < 1/10 and suspected to be related to treatment by the investigator) were stomatitis, amenorrhea, pneumonia, neutropenia, pyrexia, and gastroenteritis viral.

The below table shows the incidence of ADRs based on pooled data in patients receiving everolimus in the TSC studies (including both the double-blind and open-label study and extension periods). ADRs are listed according to MedDRA system organ class. Frequency categories are defined using the following convention: very common (\geq 1/10); common (\geq 1/100 to < 1/10); uncommon (\geq 1/1,000 to < 1/100); rare (\geq 1/10,000 to < 1/10,000); very rare (< 1/10,000); not known (cannot be estimated from the available data). Within each frequency grouping, ADRs are presented in order of decreasing frequency.

Infections and infestations

Very common - Upper respiratory tract infection, nasopharngitis, sinusitis, pneumonia

Common - Otitis media, urinary tract infection, pharyngitis, cellulitis,

pharyngitis streptococcal, gastroenteritis viral, gingivitis

Uncommon - Herpes zoster, bronchitis viral

Blood and lymphatic system disorders

Common - Neutropenia, anemia, leukopenia, lymphopenia, thrombocytopenia

Immune system disorders

Uncommon - Hypersensitivity

Metabolism and nutrition disorders

Very common - Hypercholesterolemia

Common - Hyperlipidemia, decreased appetite, hypophosphatemia, hypertriglyceridemia

Psychiatric disorders

Common - Insomnia Uncommon - Aggression

Nervous system disorders

Common - Headache, dysgeusia

Vascular disorders

Common - Hypertension, lymphedema

Respiratory, thoracic and mediastinal disorders Common - Cough, epistaxis

Uncommon - Pneumonitis

Gastrointestinal disorders

Very common - Stomatitis

Common - Diarrhea, nausea, vomiting, abdominal pain, oral pain, flatulence, constipation,

gastritis

Skin and subcutaneous tissue disorders

Very Common - Acne

Common - Rash, dermatitis acneiform, dry skin

Uncommon - Angioedema

Renal and urinary disorders

Common - Proteinuria

Reproductive system and breast disorders

Very Common - Amenorrhea C, menstruation irregular C,

Common - Menorrhagia, vaginal hemorrhage, ovarian cyst, menstruation delayed C

General disorders and administration site conditions

Common - Fatigue, pyrexia, irritability

Investigations

Common - Blood lactate dehydrogenase increased, blood luteinizing hormone increased

Uncommon - Blood follicle stimulating hormone increased

Includes very common: stomatitis, mouth ulcerationaphthous stomatitis; uncommon: gingival pain, glossitis, lip ulceration.

Includes common: rash, rash erythematous.

Includes uncommon: erythema, rash macular, rash maculo-papular, rash generalized.

Frequency is based upon number of women age 10 to 55 years of age in the safety pool.

6.3.2 Management of Infections

Everolimus has immunosuppressant properties and may predispose patients to bacterial, fungal, viral or protozoal infections, including infections with opportunistic pathogens. Patients taking everolimus are therefore at an increased risk of infection. In oncology patients, some infections have been severe, and rarely have had a fatal outcome. Physicians should be aware of the increased risk of infection, and should warn patients and their caregivers to be vigilant for signs and symptoms of infection, and to seek medical attention immediately should such signs or symptoms occur. Treat pre-existing infections prior to starting treatment with everolimus. Should an infection occur, anti-infective should be prescribed as clinically appropriate, and in the case of clinically significant infection, consideration should be given to withholding study medication until resolution of the infection.

As everolimus is an immunosuppressant, live vaccinations should be avoided (as recommended by the Center for Disease Control) (FluMist®, MMR, Varicella, human papillomavirus or HPV, rotavirus or rotarix vaccine, smallpox or vaccinia, rabies vaccine, yellow fever, typhoid Ty21a and BCG). It is okay and recommended for

participants to receive a flu shot every year (unless contraindicated) as that is an inactivated vaccine. This precaution pertains to the risk for inadequate antibody response more than risk for disease from the immunization.

6.3.3 Management of Skin Toxicity

For patients with grade 1 toxicity, no specific supportive care is usually needed or indicated. Rash must be reported as an AE. Patients with grade 2 or higher toxicity may be treated with the following suggested supportive measures at the discretion of the investigator: oral minocycline, topical tetracycline, topical clindamycin, topical silver sulfadiazine, diphenhydramine, oral prednisolone (short course), topical corticosteroids, or pimecrolimus.

6.3.4 Management of Hypersensitivity Reactions

Hypersensitivity reactions manifested by symptoms including, but not limited to, anaphylaxis, dyspnea, flushing, chest pain or angioedema (e.g. swelling of the airways or tongue, with or without respiratory impairment) have been observed with everolimus.

6.3.5 Angioedema with Concomitant Use of Angiotensin-Converting Enzyme (ACE) Inhibitors

Patients taking concomitant ACE inhibitor therapy may be at increased risk for angioedema.

6.3.6 Renal Failure Events

Cases of renal failure (including acute renal failure), some with fatal outcome, occurred in patients treated with everolimus. Renal function of patients should be monitored particularly where patients have additional risk factors that may further impair renal function. Elevations of serum creatinine, usually mild, and proteinuria have been reported in patients taking everolimus. Monitoring of renal function, including measurement of blood urea nitrogen (BUN), urinary protein, or serum creatinine, is recommended prior to the start of everolimus therapy and periodically after.

6.3.7 Management of Mouth Ulcers/Stomatitis/Oral Mucositis

Stomatitis/oral mucositis/mouth ulcers due to everolimus should be treated using appropriate locally available supportive care. Please note that investigators in earlier trials have described the oral toxicities associated with everolimus as mouth ulcers, rather than mucositis or stomatitis. If your examination reveals mouth ulcers rather than a more general inflammation of the mouth, please classify the adverse event as such. Please follow the paradigm below for treatment of stomatitis/oral mucositis/mouth ulcers:

- 1. For mild toxicity (grade 1), use conservative measures such as **non-alcoholic mouth wash or salt water** (0.9%) mouth wash several times a day until resolution.
- 2. For more severe toxicity (grade 2 in which case patients have pain but are able to maintain adequate oral alimentation, or grade 3 in which case patients cannot maintain adequate oral alimentation), the suggested treatments are topical analgesic mouth treatments (i.e., local anesthetics such as benzocaine, butyl aminobenzoate, tetracaine hydrochloride, menthol, or phenol) with or without topical corticosteroids, such as triamcinolone oral paste 0.1% (Kenalog in Orabase[®]).
- 3. Agents containing hydrogen peroxide, iodine, and thyme derivatives may tend to worsen mouth ulcers. It is preferable to avoid these agents.
- 4. Antifungal agents must be avoided unless a fungal infection is diagnosed. In particular, systemic imidazole antifungal agents (ketoconazole, fluconazole, itraconazole, etc.) should be avoided in all patients due to their strong inhibition of everolimus metabolism, therefore leading to higher everolimus exposures. Therefore, topical antifungal agents are preferred if an infection is diagnosed. Similarly, antiviral agents such as acyclovir should be avoided unless a viral infection is diagnosed.

For additional details about the treatment of stomatitis as an everolimus adverse drug reaction (ADR), see the 7904 Study Manual of Procedures.

6.3.8 Management of Hyperlipidemia and Hyperglycemia

Management of hyperlipidemia should take into account the pre-treatment status and dietary habits of the patient. Blood tests to monitor hyperlipidemia must be taken in the fasting state. Hyperlipidemia and hypertriglyceridemia should be treated according to local best clinical practice. Grade 3 hypercholesterolemia (> 400 mg/dL or 10.34 mmol/L) or grade 3 hypertriglyceridemia (>5 × ULN) should be treated as clinically indicated with a 3-hydroxy-3-methyl-glutaryl (HMG)-CoA reductase inhibitor (e.g. atorvastatin, pravastatin) or appropriate lipid-lowering medication, in addition to diet. Patients should be monitored clinically and through serum biochemistry for the development of rhabdomyolysis and other adverse events as required in the product label/data sheets for HMG-CoA reductase inhibitors.

Note: Concomitant therapy with fibrates and an HMG-CoA reductase inhibitor is associated with an increased risk of a rare but serious skeletal muscle toxicity manifested by rhabdomyolysis, markedly elevated creatine phosphokinase (CPK) levels and myoglobinuria, acute renal failure and sometimes death. The risk versus benefit of using this therapy should be determined for individual patients based on their risk of cardiovascular complications of hyperlipidemia.

Grade 3 hyperglycemia has been observed in patients receiving everolimus therapy. In almost all cases the affected patients had an abnormal fasting glucose at baseline. Based on this finding, it is suggested that optimal glucose control should be achieved before starting a patient on study drug, and that glucose control should be monitored during the trial. More frequent monitoring is recommended when everolimus is co-administered with other drugs that may induce hyperglycemia.

6.3.9 Management of Diarrhea

Diarrhea attributed to everolimus toxicity may be treated with supportive care, such as loperamide, initiated at earliest onset (for example, 4 mg orally followed by 2 mg orally every 2 hours until resolution of diarrhea). Other medications for diarrhea may be used as needed.

6.3.10 Dosing Modifications In Case of Treatment Related Toxicities

Table 3 Criteria for dose modification/re-initiation in case of toxicity suspected to be related to study treatment

Toxicity	Actions
Pneumonitis	See Table 5
Hyperlipidemia and/or hypertriglyceridemia	Any grade: Treat according to best clinical practice. No specific dose reductions are needed.
Hyperglycemia	Any grade: Treat according to best clinical practice. No specific dose reductions are needed.
Stomatitis	Grade 2: Interrupt study drug until resolution to ≤ grade 1. Restart at same dose. Grade 3: Interrupt study drug until resolution to ≤ grade 1. Reintroduce study drug at the next lower dose level**. Discontinue study drug if stomatitis does not recover to ≤grade 1 within 4 weeks. Grade 4: Discontinue study drug

Other toxicities	Grade 2 and 3: Interrupt administration until resolution to ≤grade 1. Restart at same dose.
	Grade 4: Hold study drug until recovery to ≤ grade 1. Reintroduce study drug at the lower dose level**, if available.
Toxicity requiring interruption for > 6 weeks	Permanently discontinue treatment.
No specific dose adjustments are recommended for Grade 1 toxicity. However, physicians should always	

manage patients according to their medical judgment based on the particular clinical circumstances.

**To determine the next lowest dose level, please refer to Table. 5.

Table 4 Dose modification guidelines for hematologic toxicities

Toxicity	Actions		
Thrombocytopenia Platelet Count	 ≥ 75000/mm³: No change 50000/mm³ to 75000/mm³: Hold study drug until recovery to ≥ 75000/mm³. Reintroduce study drug at the same dose level < 50000/ mm³: Hold study drug until recovery to ≥ 75000/mm³. Reintroduce everolimus at the next lower dose level, if available 		
Absolute Neutrophil Count (ANC)	 ≥ 1000/ mm³: No change 500/mm³ to 1000/ mm³: Hold study drug until recovery to ≥ 1000/mm³. Reintroduce study drug at the same dose level < 500/ mm³: Hold until recovery to ≥ 1000/ mm³. Reintroduce everolimus at the next lower dose level, if available. 		
Febrile Neutropenia	Hold further dosing until ANC ≥ 1250/mm ³ and no fever. Then resume dosing at the next lower dose level** if available.		
Toxicity requiring interruption for >6 weeks	Permanently discontinue treatment.		
Physicians should always manage patients according to their medical judgment based on the particular clinical circumstances.			

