Grade 3	CT scan with lung windows and pulmonary function testing including spirometry, DL_{CO} , and room air O_2 saturation at rest. Repeat at least every 4-8 weeks until return to within normal limits. Bronchoscopy with biopsy and/or BAL is recommended.	Consider corticosteroids if infective origin is ruled out. Taper as medically indicated.	Hold treatment until recovery to ≤ Grade 1. May restart study treatment within 3 weeks at a reduced dose (by one level**) if evidence of clinical benefit.
Grade 4	CT scan with lung windows and required pulmonary function testing including spirometry, DL _{CO} , and room air O ₂ saturation at rest. Repeat at least every 4-8 weeks until return to within normal limits. Bronchoscopy with biopsy and/or BAL is recommended if possible.	Consider corticosteroids if infective origin is ruled out. Taper as medically indicated.	Discontinue treatment.

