7.6.1 Emergency Unblinding Treatment Assignment

In general, circumstances that might lead to emergency unblinding are rare. Most often, study drug discontinuation and knowledge of the possible treatment assignments are sufficient to treat a study patient who presents with an emergency condition. One unusual circumstance in which unblinding might be necessary is when a patient requires emergency surgery and the anesthesiologist needs to know all medications that the patient has been exposed to in order to make proper decisions about treatment and support during the surgery.

Emergency unblinding should only be done when necessary in order to treat the patient. Emergency code breaks are performed using the database, as described in the 7904 Manual of Procedures.

It is the investigator's responsibility to ensure that there is a procedure in place for emergency unblinding. The investigator will inform the patient how to contact his/her backup in cases of emergency when he/she is unavailable.

Study drug must be discontinued after emergency unblinding. The investigator is not allowed to place emergency unblinded patients into open-label everolimus therapy.

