7.7 Treating the Patient

7.7.1 Study Drug Administration

Everolimus or placebo will be dispensed by the study center personnel on an outpatient basis. Patients will be provided with study drug at Visit 2 (Baseline), and each subsequent on-site visit for self-administration at home.

The first dose of everolimus or placebo must be taken within 7 days of Visit 2 (Baseline). Patients will be instructed to take everolimus or placebo by mouth regularly, with the dose being taken at the same time in the morning every day. Everolimus or placebo tablets should be swallowed whole with a glass of water. The tablets should not be chewed or crushed. Any dietary habits around the time of everolimus or matching placebo intake should be as consistent as possible throughout the study. The extent of absorption of everolimus through topical exposure is not known. Therefore, patients/caregivers are advised to avoid contact with the everolimus or placebo tablets and should wear gloves and should wash their hands thoroughly before and after administration. If vomiting occurs, no attempt should be made to replace the vomited dose. Patients should be instructed that if they miss a dose one day, they must not take any extra dose the next day.

Patients should be requested to bring their unused study drug, including the empty blister packs, to the clinic at each visit.

Patients will receive treatment with study drug for 6 months or until the occurrence of unacceptable toxicity or the investigator or patient decides that continuation is not in the best interest of the patient. Interruption for toxicity should follow the instructions in Table 3.

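### Table 3 has no hypersensitivity row, so the recommended default after a severe drug-related reaction is to restart study drug, and nothing specific to hypersensitivity requires a stop

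*Combined protocol and SAP*

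**What the plan says.** Section 6.3.4 describes the reactions: "Hypersensitivity reactions manifested by symptoms including, but not limited to, anaphylaxis, dyspnea, flushing, chest pain or angioedema". It notes that they have been seen with everolimus and ends there. Section 6.3.5 adds one sentence, "Patients taking concomitant ACE inhibitor therapy may be at increased risk for angioedema", again without an action.

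Table 3 (6.3.10) applies to any toxicity thought to be caused by study treatment. Its rows are pneumonitis (referred to Table 5), raised lipids, hyperglycemia, stomatitis, other toxicities, and interruptions longer than 6 weeks. For other toxicities it says "Grade 2 and 3: Interrupt administration until resolution to ≤grade 1. Restart at same dose"; at Grade 4, drug is held until recovery and then given again at a lower level if there is one. Section 7.7.1 points to this table: "Interruption for toxicity should follow the instructions in Table 3".

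For stomatitis, Grade 3 goes to the next lower dose, and the row continues "Discontinue study drug if stomatitis does not recover to ≤grade 1 within 4 weeks. Grade 4: Discontinue study drug". For Grade 3 pneumonitis, Table 5 holds treatment and then says "May restart study treatment within 3 weeks at a reduced dose (by one level) if evidence of clinical benefit"; at Grade 4 it discontinues.

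**The concern.** Anaphylaxis and angioedema with airway swelling are named in 6.3.4 as reactions seen with this drug, yet the protocol gives no specific instruction for them. A site looking for one is left with the catch-all row, which interrupts and then resumes. If the suspected reaction was severe, the written default gives the patient the suspected agent again, self-administered at home under 7.7.1. The protocol spells out a stop at Grade 4 for two other toxicities but not for this one. What is at stake is patient safety, in a population that includes children from age 5.

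**Working it through.** There is no stated figure to reproduce. The check sets the texts side by side.

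**Step 1: which row applies.** Table 4 is hematologic and Table 5 is non-infectious pneumonitis. Within Table 3, lipids, glucose and stomatitis do not fit. The rows left are other toxicities and the general stop for interruptions over 6 weeks. No sentence assigns hypersensitivity to the other-toxicities row; it gets there by elimination.

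**Step 2: compare the rules by grade.**

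| Grade | Other toxicities (Table 3) | Stomatitis (Table 3) | Pneumonitis (Table 5) |
|---|---|---|---|
| 3 | Hold, then same dose | Hold, then next lower dose; stop if not recovered in 4 weeks | Hold; may resume one level lower, only with clinical benefit |
| 4 | Hold, then lower dose if available | Stop | Stop |

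The catch-all row is less strict than both comparators at both grades. At Grade 2 it matches stomatitis, so the comparison does not rest on Grade 2. The dose resumed at Grade 3 may already have been lowered by an earlier adjustment.

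**Step 3: compare with Table 4.** After platelets below 50,000/mm³, neutrophils below 500/mm³ or febrile neutropenia, Table 4 also resumes drug at the next lower level. Lower-dose reintroduction after severe toxicity is therefore not peculiar to the catch-all row.

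**Step 4: look for a stop elsewhere.**
- Exclusion 2 in 4.6.2 bars known hypersensitivity at entry; it is not an on-treatment rule.
- Section 7.7.3 allows reintroduction if recovery takes less than 6 weeks, so the 6-week stop misses any reaction that settles sooner.
- Section 7.6.1 makes discontinuation mandatory only after emergency unblinding. The open-label phase has no blind to break, so that stop cannot apply there, although 4.4 makes treatment the same in both phases.
- Under 13.4 the medical monitor makes the final causality decision on a serious event, and under section 15 the medical review officer reviews events. Neither section requires a decision before a restart.

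**Step 5: frequency.** Section 6.3.1 places hypersensitivity in the uncommon category (at least 1/1,000 and under 1/100). That category is not split by grade and pools double-blind, open-label and extension exposure, so it yields no 6-month rate of Grade 3 or higher reactions.

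**Step 6: effect of a mandatory stop on the primary endpoint.** With 20 patients per arm, one extra stop is 1/20 = 5 percentage points. Two in the same arm, with none in the other, are 2/20 = 10 points, which is the difference that 17.1 treats as meaningful.

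**The case against.** The strongest reply is that the restart rows are reached only after an investigator has chosen to interrupt. Section 7.7.6 separates interruption from permanent discontinuation, and 4.3 and 7.7.1 end treatment for unacceptable toxicity. An investigator who judges anaphylaxis unacceptable stops the drug, and Table 3 never comes into play. Section 6.3 calls the table a set of recommendations, and its own note tells physicians always to "manage patients according to their medical judgment based on the particular clinical circumstances". Section 6.2 brings the medical review officer into safety dose changes as appropriate. Section 7.6.1 also leans toward stopping: "Most often, study drug discontinuation and knowledge of the possible treatment assignments are sufficient to treat a study patient who presents with an emergency condition".

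All of this stands, and it rules out a reading that some may be tempted to make, namely that the protocol obliges a site to rechallenge after anaphylaxis. It does not. But each of these provisions permits a stop and none requires one. The sentence in 7.6.1 describes usual practice and gives no instruction. The same discretion covers stomatitis and pneumonitis, and the protocol still wrote explicit stops for those.

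A second reply is that the Manual of Procedures or the Investigator's Brochure may hold the missing rule. Neither was available for this review, so that remains possible. Section 6.3.7 refers the reader to the Manual for stomatitis; 6.3.4 refers to neither document.

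**Conclusion.** The concern holds in a limited form. By elimination, the recommended default for a suspected drug-related hypersensitivity reaction is the same dose after Grade 2 or 3 and a lower dose after Grade 4. That is less strict than the Grade 3 and 4 rules for stomatitis and pneumonitis. Discretion makes an actual rechallenge less likely but leaves the default in place and puts no required stop beside it. It should be fixed; confidence is moderate, because the Manual and Brochure could not be checked.

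Three stronger inferences are not supported:
- That exclusion 2 contradicts Table 3. It governs entry only.
- That resuming drug after severe toxicity is unique to this row. Table 4 does so too, at a lower level.
- That the uncommon category can be turned into a chance of anaphylaxis in this trial. With no Grade 3 or higher rate in the documents, the argument rests on the severity of one such event.

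**What to change.** Exclude hypersensitivity, anaphylaxis and angioedema from the other-toxicities row. Add a Table 3 row, cross-referenced in 6.3.4 and 6.3.5 and applying to both the blinded and the open-label phase: permanently discontinue, without rechallenge, for anaphylaxis, airway angioedema, or any hypersensitivity reaction of Grade 3 or higher suspected to be related to study drug. The Grade 3 threshold is a clinical proposal, since the documents set none for patients on treatment; the clinical team should confirm it and write the Grade 2 rule. If the Manual or Brochure already contains such a rule, cite it in 6.3.4 and Table 3 instead.

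The cost is one row and its cross-references in an amendment, with no new data or procedures. The downside is that an occasional patient, possibly on placebo, who could have tolerated a restart is stopped and counts as a side-effect drop-out. Section 7.7.6 already has such a stop recorded as due to an adverse event, so no new coding is needed.
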